The effects of E+shots on mood, cognitive function, heart rate, blood pressure, cortisol and fine motor task performance NCT #16-05

*Design:* This is a double blinded cross-over experiment with repeated measures on treatment (25mg caffeine vs 100mg caffeine vs e+shots) and Time (Time 1 (pre-beverage), Time 2, Time 3, Time 4). Previous night's sleep and occupation may be used as a co-variate in the statistical analysis.

#### Procedure:

### Screening day:

- Potential subjects will complete an initial online screening using questionnaires that will be posted on surveymonkey.com. The appendices listed below are the questionnaires that are posted in the survey.
- The survey may be accessed through the tiny URL, QR code, or through a link that will be provided by the researcher.
  - o Appendix G- A demographic and medical history questionnaire
    - As seen in the exclusion criteria all subjects who use prescription or over the counter medications for chronic medical conditions will not be allowed to participate in the study, with the exception of people taking oral contraceptives.
    - Subjects who are taking a prescription or over the counter medication for an acute health condition may be asked to participate in the study after they are no longer taking the medication or they will be given the option to drop out of the study.
  - Appendix H- Profile of Mood Survey (POMS) brief form
    - We will calculate the energy score of the POMS.
    - If the energy score is >=13 then the potential subject will be eliminated from the study
  - o Appendix I- Caffeine consumption questionnaire
    - Using the data from this survey subjects who consume >=200mg of caffeine per day will be eliminated from this study
  - Appendix J- Food frequency questionnaire
    - Using the data from this survey subjects who consume >=150 servings of polyphenols per month will be eliminated from the study
  - Appendix K- Mental and Physical State and Trait Energy and Fatigue Scales (see appendix R for approval to use questionnaire)
    - The objective of this scale is to control of cognitive bias by asking questions regarding use of prescription drugs and using a different energy and fatigue scale to measure energy levels.
    - A score of >10 on the energy scale will eliminate the potential subject
    - This scale also measures physical and mental activity levels which will be used in the statistical analysis as covariates
  - Appendix L- Pittsburgh sleep quality index
    - This survey will be used to measure sleep time and sleep quality of potential subjects.
    - Sleep will be used to determine eligibility on day of testing
    - Sleep quality will be used as a covariate in the statistical analysis
- After completion of survey, a research assistant will verify that the subject is eligible for the study and will contact them via the email that is provided by the subject.

Researchers will review the results of all of these questionnaires to confirm if a potential subject met the criteria or did not. Potential subjects who met the criteria will be asked via e-mail to schedule a mutually convenient date for "familiarization day" (see below) to confirm eligibility, perform the second informed consent, and begin participating in the study (appendix S). Potential subjects who did not meet the criteria will be notified and thanked for their time via e-mail (appendix T).

### Day 1: Familiarization day

To reduce experimental error that may occur due to learning effect, subjects will be asked to come in for approximately 40 minutes to familiarize themselves with the protocol. This time will also be used to confirm their

eligibility by confirming the accuracy of the information entered in the initial screening questionnaires, obtain informed consent and begin the procedure. The following will be the procedure for the day:

- We will measure subjects' height and weight using a stadiometer and scale, as well as BP. We will
  eliminate subjects who have a BMI >30.0 and resting systolic BP >140mmHg or resting diastolic BP
  >90mmHg.
- Subjects will then go through a test battery of:
  - Computerized cognitive battery (see appendix V for description):

•	Serial subtraction of the number three	2 minutes
•	Serial subtraction of the number seven	2 minutes
•	Continuous performance test (CPT)	5 minutes
•	Bakan rapid visual processing task	16 minutes

Self-reported measures (see Appendix N, O, H)

Motivation to perform cognitive tasks
 Visual analog scales of mental energy and fatigue
 Profile of Mood State fatigue and vigor scales
 3 minutes

Physiological measures

Resting heart rate and blood pressure 1 minute

Fine motor skills

9-hole peg test5 minutes

Total time 36 minutes

Subjects who are excluded or choose to drop out on this date will not receive the \$5 compensation.

### Days 2-4

Testing days 2-4 will be similar except subjects will consume a different beverage daily (list the 3 different beverages). To reduce bias, the days that subjects will consume a certain beverage will be randomized using a randomizing software on randomizer.org. All beverages are labeled as products, A, B or C and are blinded for the researcher. Information regarding all beverages is listed in Table 1.

On each day subjects will complete the following procedure:

Subjects will complete a pre-screening questionnaire on each day. The questionnaire will contain the following surveys

- Appendix M- 24 hour drug/medicine/supplement recall
  - This survey asks for a 24-hour prescription medication, over the counter medication, and supplement recall. Because of the potential for cognitive bias (as described above) we are asking the subjects for the names of any medications they may be taking. In our past studies there were a few subjects that initially reported that they were not taking any prescription or over the counter medications (either for a chronic or acute health condition) however, during the daily testing procedures when we asked these subjects specifically what medications they were taking they listed certain medications. By asking specifically what medications the subjects are taking we are hoping to reduce the risk of cognitive bias and appropriately eliminate subjects who are taking prescription or over the counter medications while they are in the study.
    - The survey asks if subjects are taking an oral contraceptive and specifically what the name of the oral contraceptive is. The information on the specific type of oral contraceptive is needed as certain oral contraceptives have an impact on mood while others do not (Kahn & Halbriech, 2005).
  - We are also asking for caffeine intake and time of intake. To control for cognitive bias we are asking for time of intake.
- Appendix N- Sleep questionnaire
  - o This survey will be used to determine the amount of sleep the subject had the night before.
  - This survey will serve two purposes
    - If subjects had > or < ±2 hours of sleep from their normal sleep then they will be rescheduled. Their normal sleep will be determined using Appendix L. Their normal sleep will be given to the researcher in charge of collecting data prior to subject's arrival.

- If the subject is eligible for the study, the sleep may be used as a covariate in the data analysis.
- Appendix Q- What I ate today
  - o This survey will be used to determine what the subject ate the day of the testing
  - The information may be used during data analysis to estimate methyxanthine intake

After subjects have been pre-screened for the day, the research assistant will collect saliva using the drool down method. To collect data using the drool down method subjects must collect saliva in their mouth and let it drool down through a straw into a 15mL saliva collection tube. After ~2mL of saliva has been collected, saliva will be stored in a chest filled with ice, prior to transportation to a freezer that is set at -80F.

After saliva collection, subjects will go through the following mental energy test battery (see table 2). Consumption of beverages and subsequent mental energy test batteries will be administered as outlined in table 2. *Dependent Variables* 

1) Computerized cognitive battery:

a.	Serial subtraction of the number three	2 minutes
b.	Serial subtraction of the number seven	2 minutes
c.	Continuous performance test (CPT)	5 minutes
d.	Bakan rapid visual processing task	16 minutes

2) Self-reported measures

a.	Motivation to perform cognitive tasks (Appendix N)	1 minute
b.	Visual analog scales of mental energy and fatigue (Appendix O)	1 minute
c.	POMS (Appendix H)	3 minutes

3) Physiological measures

a. Resting heart rate and blood pressure 1 minute

4) Fine motor skills

a. 9-hole peg test 5 minutes

Total time 36 minutes

The 9-hole peg test is used to measure finger dexterity. The test is administered by asking the client to take the pegs from a container, one by one, and place them into the holes on the board, as quickly as possible. Participants must then remove the pegs from the holes, one by one, and replace them back into the container.

After completion of the mental test batteries and procedure outlined in Table 2, subjects saliva will be collected again using the drool down method.

Table 1

Ingredient Name	Current E-shot	Placebo w/ Caffeine	Placebo w/o Caffeine
Water	4oz	4oz	4oz
LERA Herbal Extract Complex	Proprietary	0	0
Green Tea (Camellia sinensis) Leaf Extract (50% Caffeine)	Proprietary	0	0
Yerba Mate Extract (25% Caffeine)	Proprietary	0	0
D-Ribose	25.000 mg	0	0

Synthetic Caffeine	0.000	100.000mg	0
Apple Juice Concentrate 70 Brix	Trace amounts	Trace amounts	Trace amounts
	Trace amounts	Trace amounts	Trace amounts
Glycerin (vegetable source)	Trace amounts	Trace amounts	Trace amounts
Stevia (Stevia rebaudiana) Leaf Extract, 97%	Trace amounts	Trace amounts	Trace amounts
Pomegranate Juice Concentrate ME-3605	Trace amounts	Trace amounts	Trace amounts
Masking Flavor Nat ME-1748	Trace amounts	Trace amounts	Trace amounts
Pomegranate-Berry Flavor Nat ME-2569	Trace amounts	Trace amounts	Trace amounts
Mint Flavor Nat WONF ME-2759	Trace amounts	Trace amounts	Trace amounts
Sodium Citrate	Trace amounts	Trace amounts	Trace amounts
Malic Acid	Trace amounts	Trace amounts	Trace amounts
Potassium Sorbate	Trace amounts	Trace amounts	Trace amounts

# Table 2

Time (minutes)	Event	Test Phase
0 – 36	Test battery	Trial 1
36-66	Beverage then seated rest	
66-102	Test battery	Trial 2
102-112	Rest	
112-148	Test battery	Trial 3
148-158	Rest	
158-194	Test battery	Trial 4

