# Analysis of outcomes:

Hypothesis will be tested using a two factor (3 beverages x 4 times) repeated measures ANCOVA on change scores (Times 4, 3 and 2 minus Time 1 are the 4 Times). The primary interest will be whether there is a statistically significant main effect for time or interaction. Focused contrasts between specific time points as follow up tests.

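### Test days may be consecutive with no stated washout, so beverage-specific carry-over that same-day change scores do not remove can bias the beverage contrasts

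*Combined protocol and SAP*

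**What the plan says.** The Design paragraph describes a "double blinded cross-over experiment with repeated measures on treatment (25mg caffeine vs 100mg caffeine vs e+shots". Under Days 2-4, "Testing days 2-4 will be similar except subjects will consume a different beverage daily". Order is handled by one sentence: "the days that subjects will consume a certain beverage will be randomized using a randomizing software on randomizer.org". Balance over the possible orders is not mentioned. Neither a minimum interval between test days nor a fixed start time appears in the visible text.

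Sleep on the night before a test day has two uses. It is a gate: "If subjects had > or < ±2 hours of sleep from their normal sleep then they will be rescheduled". It is also a possible adjustment: "Previous night's sleep and occupation may be used as a co-variate in the statistical analysis". On caffeine, the test-day recall states "We are also asking for caffeine intake and time of intake", with no abstinence or rescheduling rule attached. Screening admits regular users below a limit: "subjects who consume >=200mg of caffeine per day will be eliminated from this study".

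Analysis of outcomes specifies a two-factor (beverage by time) "repeated measures ANCOVA on change scores (Times 4, 3 and 2 minus Time 1 are the 4 Times". It names no period, sequence or carry-over term.

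**The concern.** If the three test days run back to back, the night before Days 3 and 4 is the night after a stimulant drink from the trial. Sleep on that night may then be partly a result of the preceding beverage, yet it decides whether the subject is tested. A subject whose sleep shifts by more than 2 hours is rescheduled and so gets a longer gap. One whose sleep shifts by 1.9 hours is tested the next day. The gap between beverages therefore depends on response to the earlier one.

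Randomising the order does not cancel carry-over, because a beverage is never preceded by itself: each is preceded only by the other two. If the beverages leave different after-effects, the contrasts between them can be distorted. A larger sample does not reduce that bias, and the planned model could neither detect it nor adjust for it.

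**Working it through.** The documents give no washout length, carry-over size, SD or sample size, so there is no planned figure to reproduce. Two checks are possible.

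**1. How much carry-over survives in the contrasts**

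Inputs: three beverages and three test days (Design; Days 2-4); outcome is change from the same day's Time 1 (Analysis of outcomes). Assumptions: all six orders are used equally, and carry-over reaches only the next test day.

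For the day after beverage X, let *a*(X) be the carry-over at Time 1 and *b*(X) the carry-over at a later time. The change score carries *d*(X) = *b*(X) − *a*(X).

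Over the six orders, each beverage is preceded by each of the other two in 2 of 6 orders and by none in 2 of 6. With Z the third beverage:

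- mean carry-over in X's data = [*d*(Y) + *d*(Z)]/3
- mean carry-over in Y's data = [*d*(X) + *d*(Z)]/3
- bias in (X minus Y) = [*d*(Y) − *d*(X)]/3

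With L the size of a beverage's carry-over:

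| Type of carry-over | *d* | Bias in (X minus Y) |
|---|---|---|
| Constant through the visit | L − L = 0 | 0 |
| Equal for all beverages | same for all | 0 |
| Halves after Time 1 | L/2 − L = −L/2 | [L(X) − L(Y)]/6 |
| Absent at Time 1, alters later response | L − 0 = L | [L(Y) − L(X)]/3 |

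Least-squares fits with subject effects on all six orders gave the same values (0, 0, 0.167 and −0.333 when L(X) = 1 and L(Y) = 0, with the equal case 0). Adding a period effect did not change them. If only three cyclic orders were used, one beverage would follow a given other beverage in 2 of 3 orders, and the bias could reach 2/3 of L (0.667 in the fit).

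**2. Residual caffeine**

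Inputs: 100 mg in the caffeine beverage (Design; Table 1); beverage at minute 36 and Trial 4 starting at minute 158 (Table 2). Assumptions: test days start exactly 24 h apart; half-lives of 5, 10 and 12 h, which are not from the documents.

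Gap to the next Time 1 = 24 h − 36 min = 23.4 h. Gap to the start of the next Trial 4 = 23.4 h + 158 min = 26.03 h. With one day between test days, the gap to Time 1 = 48 h − 36 min = 47.4 h. Residual = 100 × 2^(−gap/half-life) mg.

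| Assumed half-life | Next-day Time 1 | Next-day Trial 4 | Fall during visit | Time 1 with one day between |
|---|---|---|---|---|
| 5 h | 3.9 mg | 2.7 mg | 1.2 mg | 0.14 mg |
| 10 h | 19.8 mg | 16.5 mg | 3.3 mg | 3.7 mg |
| 12 h | 25.9 mg | 22.2 mg | 3.7 mg | 6.5 mg |

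Most of the residual is already present at Time 1 and so lies in the baseline that is subtracted. The last column shows only how spacing matters; it does not support any particular interval.

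**The case against.** The strongest reply has four parts.

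- **Consecutive days are not established.** Days 2-4 may be visit numbers. Day 1 is booked by agreement, the same section elsewhere uses *daily* loosely for what happens at each session, and visits can be rescheduled. The consent pages and appendices were not available and might state the spacing. This stands as a limit on the claim: a reader might infer that next-day dosing is planned, but the text only permits it. The point survives, because nothing visible prevents it.
- **Same-day change scores protect the contrasts.** This also stands in part. A reader might infer that the contrasts are certainly biased. The documents do not support that: the bias is zero if carry-over is constant through the visit or equal across beverages.
- **Other safeguards exist.** Order is randomised, the gate removes the largest sleep disturbances, recall captures caffeine and its timing, and a sleep covariate could absorb part of the sleep route. But shifts of up to 2 hours pass the gate, the covariate is optional, and no action follows from the caffeine recall.
- **Residual caffeine is small.** This stands. Daily intake just below 200 mg is admitted with no visible abstinence rule, so non-study caffeine could exceed the residual. A reader might also set the slow-end residual against the 25 mg beverage. That comparison is not safe: the Design paragraph names a 25 mg caffeine beverage, while Table 1 lists a placebo without caffeine and with no synthetic caffeine. Those two places must be reconciled.

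**Conclusion.** The concern holds in conditional form. The visible plan permits back-to-back test days, lets sleep on a possibly treatment-affected night decide when a subject is tested, and has no model term that could reveal carry-over. Bias in a beverage contrast requires carry-over that differs between beverages and either changes during the visit or alters the response to the new beverage. In the cases worked, with balanced orders, it is then 1/6 (sign reversed) to 1/3 of the between-beverage difference in carry-over, and possibly more if the orders are unbalanced.

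These are fractions of an unknown quantity. The documents give no effect of any beverage on sleep, or of sleep on the outcomes, so the bias cannot be expressed in outcome units. Sleep is the more plausible route; residual caffeine is minor. The point is worth acting on because carry-over of this kind cannot be repaired or detected after data collection, whereas preventing it is cheap.

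**What to change.** Under Days 2-4, replace *daily* with a rule that test days are not consecutive, using a minimum interval that the sponsor sets and justifies for these products. The aim is that the pre-test night is never the night after a study beverage. Apply the same rule to rescheduled days.

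State that the six orders are used equally, and add a period effect to the model under Analysis of outcomes. The period effect separates day-to-day trends from beverage differences; it does not remove carry-over, so it does not replace the spacing rule.

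Cost: one scheduling sentence, one sentence on order and one model term, with no added visits or measurements. Three non-consecutive test days span at least five calendar days instead of three, and longer if the sponsor's interval is longer. A few more drop-outs are possible.

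### Beverage orders are not stated to be balanced and the model has no test-day term, so a practice gain that shrinks over the three test days would cost precision, not validity, in the beverage and beverage x time comparisons.

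*Combined protocol and SAP*

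**What the plan says.** The Design paragraph describes a crossover with repeated measures on treatment and Time: "This is a double blinded cross-over experiment with repeated measures on treatment". Under Days 2-4, each subject takes one of the three beverages on each of three test days, and "the days that subjects will consume a certain beverage will be randomized using a randomizing software on randomizer.org". Nothing there or elsewhere requires the six orders, or the beverages on a given day, to be balanced.

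The section Analysis of outcomes specifies a "two factor (3 beverages x 4 times) repeated measures ANCOVA on change scores", with the note that "Times 4, 3 and 2 minus Time 1 are the 4 Times". Primary interest is in a "statistically significant main effect for time or interaction". Follow-up is given as "Focused contrasts between specific time points as follow up tests".

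The covariates named are previous night's sleep and occupation (Design: "sleep and occupation may be used as a co-variate in the statistical analysis"; sleep again under Days 2-4), and activity levels and sleep quality (Screening day). None of them stands for test day.

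The Familiarization day section gives one run of the battery, with the purpose "To reduce experimental error that may occur due to learning effect". Table 2 then schedules four batteries on each of the three test days, 12 in all.

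**The concern.** The plan itself recognises learning and answers it with a single practice run, which may reduce learning without ending it. Suppose performance still improves within a day, and improves more on the first test day than on the third. Each subject's change scores then contain a practice component that depends on the day. Beverage is tied to day within a subject, so the component falls on different beverages in different subjects. With no test-day term in the model, it goes into the residual. If the orders are also unbalanced by chance, it goes into the estimated beverage differences as well.

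At stake is power for the beverage comparison, which is the trial's purpose, and for the interaction, which is one of the two tests of primary interest. Only practised tasks are affected. The documents do not say which these are; the cognitive battery and the peg test are the plausible ones.

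**Working it through.** **Inputs.** From the documents: three beverages, three test days, one familiarisation battery, four batteries per test day, change from the same day's Time 1, and no test-day term. The documents give no n, SD, effect size or practice size, so there is no figure of the plan's to reproduce. Assumed: n=30 (also 18); effect 0.75 SD; SD = within-subject SD of a day's mean change score, set to 1; two-sided 5%. The gap is the mean practice gain on the first test day minus that on the third, in the same SD.

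**Step 1: variance.** With balanced orders and test day modelled, a beverage difference has variance 2/n. With simple randomisation and no test-day term it is about 2(1 + S²)/n, where S² is the sample variance (divisor 2) of the three daily practice gains.

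**Step 2: size of S².** A log learning curve over 13 batteries gives mean daily gains of 0.672, 0.282 and 0.180.
- Gap: 0.672 − 0.180 = 0.492.
- Mean 0.378; squared deviations 0.0864, 0.0092 and 0.0392; so S² = 0.1348/2 = 0.0674.
- Scaled to the gap: 0.0674/0.492² = 0.279, so S² = 0.279 × gap².
- Implied mean first-day gain: 0.672/0.492 = 1.37 × gap.

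A gain that halves each day (1, 0.5, 0.25) gives S² = 0.1458 at a gap of 0.75, that is 0.259 × gap², which is nearly the same.

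**Step 3: time-averaged beverage contrast, n=30, log curve.** SE = √(2(1 + S²)/30). Power is simulated (8,000 runs per cell).

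| Gap (SD) | Implied mean first-day gain | 1 + S² | SE, formula (simulated) | Power as planned | Power after fix | Loss (points) |
|---|---|---|---|---|---|---|
| 0.25 | 0.34 | 1.017 | 0.260 (0.259) | 81% | 81-82% | 0 |
| 0.5 | 0.68 | 1.070 | 0.267 (0.266) | 79% | 81-82% | 3 |
| 1.0 | 1.37 | 1.279 | 0.292 (0.290) | 72% | 81-82% | 10 |
| 1.5 | 2.05 | 1.627 | 0.329 (0.328) | 61% | 81-82% | 21 |

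Formula and simulation agree. With the halving curve, power at gaps 0.5, 1.0 and 1.5 is 80, 72 and 60%, against 80-82% after the fix. At n=18 (log curve) it is 58, 56, 49 and 40% over the four gaps, against 59%.

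**Step 4: error rate and time effect.** Under simple randomisation, simulated type I error was 4.4% to 5.7%. The error sum of squares for the time main effect stayed at 28.9 to 29.1 at every gap, because every subject completes all three days.

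**Step 5: interaction.** The plan names four times but defines three change scores, so two readings are open.
- Change scores only, for example Time 4 minus Time 2: the practice gap in this slope is 0.344/0.492 = 0.70 of the mean gap. With the 0.75 effect in SD of that difference, n=30, power over the four gaps is 81, 81, 78, 75% (change scores correlated 0.5) or 82, 80, 74, 68% (0.7), against 81-82% after the fix. If 0.75 is instead in SD of the mean change score, power at gaps 0.5, 1.0 and 1.5 is 64, 60, 56% (0.5) or 89, 86, 79% (0.7), against about 64% and 91%.
- Time 1 as a fourth level (6 df test), n=30: 69, 65, 61, 53% against about 69%.

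**Step 6: what each half of the fix does.** SD of the estimate at n=30, gap 1.5: 0.326 with simple randomisation, 0.253 with balance only, 0.254 with balance plus test day. Balance only leaves S² in the error term, so the test is conservative: type I error is 4.6, 4.0, 2.4 and 1.2% over the four gaps, and power 81, 80, 74 and 63%. Simple randomisation plus test day gives 80% at n=30 and 56% at n=18.

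**The case against.** The strongest reply is that the plan already has three safeguards: randomised beverage days, change scores from the same day's baseline, and a familiarisation visit. Together they leave only a second-order effect. Losses of 10 points or more in the beverage contrast need a mean first-day gain of about 1.4 SD or more after familiarisation, and nothing in the documents supports a gain of that size. Of the two tests of primary interest, the time main effect is untouched, and the loss on the Time 4 minus Time 2 contrast is 1 to 2 points up to a gap of 0.5 SD. All of this stands, and it limits the weight of the point.

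Some stronger readings are tempting but do not hold:
- A reader might infer that the missing test-day term biases the beverage comparison or produces false positives. It does not: days are randomised, and type I error stays near 5%.
- A reader might infer from the conservative test that balancing without a test-day term is useless or harmful. Balance alone restores the precision of the estimate. At n=30 its power is no lower than as planned at any gap; it was lower only at n=18 with a large gap (37% against 40% at gap 1.5).
- A reader might infer that the ANCOVA cannot take test day and must be abandoned. The plan already allows previous night's sleep, which varies by day, as a covariate, so a model that carries it can carry test day.

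**Conclusion.** The point holds as a conditional loss of precision. The plan states no balance over orders and models no test day, and same-day change scores cannot remove a practice gain that shrinks over days. On the assumptions above, with n=30, the loss for the time-averaged beverage contrast is about 0 to 3 power points up to a gap of 0.5 SD, about 10 at 1.0 SD and about 20 at 1.5 SD, whether the learning curve is logarithmic or halving. It is smaller for Time 4 minus Time 2. If practice gains are equal across days, nothing is lost. Because the documents give no n, SD or practice size, they do not show where in this range the trial lies. This is an inexpensive improvement worth considering, not a flaw that would invalidate the results.

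**What to change.** 1. Allocate subjects in permuted blocks of six to the six orders (ABC, ACB, BAC, BCA, CAB, CBA), and say so under Days 2-4.
2. Add test day and test day x time to the planned analysis. One way is a linear mixed model for the three change scores, with beverage, time, beverage x time, test day, test day x time and the planned covariates as fixed effects, and subject, subject x time and subject x test day as random effects. Keep subject x test day: the three change scores of a day share one Time 1. In simulation with n=30, balanced orders and no effect, a subject intercept alone gave 20% to 26% type I error for the beverage contrast, against 5.1% with that term.

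The test-day term brings most of the gain in power; once it is in, balance adds about 1 to 3 points. Use both, since balance without the term leaves a conservative test (type I error about 1-3% at gaps of 1.0 to 1.5 SD).

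If allocation is already complete, decide before unblinding whether to add the test-day terms. For the time-averaged contrast they pay off only above a gap of about 0.4 SD (n=30) or 0.5 SD (n=18).

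Cost: a new randomisation list and 6 model degrees of freedom (2 for test day, 4 for test day x time), with no extra subjects or visits. If there is no day effect, the power cost is about 0 with balanced orders. With unbalanced orders it is about 1 point at n=30 (80.2 against 81.2%) and about 3 at n=18 (56.4 against 58.9%).

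### The plan appears to give each beverage one fixed letter for all subjects and does not say who sees it, so one correct guess or one leak about a letter would carry over to every subject.

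*Combined protocol and SAP*

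**What the plan says.** The Design statement opens with "This is a double blinded cross-over experiment" and lists three treatments: 25 mg caffeine, 100 mg caffeine and the e+shot.

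Days 2-4 sets out allocation and labelling. Each subject takes all three products: "Testing days 2-4 will be similar except subjects will consume a different beverage daily". What is randomised is the order: "the days that subjects will consume a certain beverage will be randomized using a randomizing software on randomizer.org". The label is covered by one sentence: "All beverages are labeled as products, A, B or C and are blinded for the researcher".

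The list of dependent variables in the same section includes "Resting heart rate and blood pressure 1 minute" in the battery. The battery is repeated around the drink: "Consumption of beverages and subsequent mental energy test batteries will be administered as outlined in table 2". Table 2 places Trial 1 before the beverage and Trials 2, 3 and 4 after it.

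The documents mention no subject-specific code, key holder, separate dispenser or separate assessor. They also do not say that these are absent.

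**The concern.** Three products, three letters and randomised days together suggest that a letter means the same product for every subject. Under such a scheme, what is learned about a letter from one subject applies to the next.

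Caffeine content differs between products, and vital signs are measured on site after each drink. A tester who sees both the letter and the readings could therefore come to suspect which letter is the low-caffeine product. Separately, anyone who learned the key and had the letters recorded for each session would know every subject's sequence at once.

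At stake are the outcomes most open to a tester's expectation: the peg test, and the mood, motivation and visual analog ratings so far as the tester influences how they are given.

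**Working it through.** **The labelling text.** The plan has three products and three letters. The random element is the day on which a product is taken, not the letter attached to it. Nothing in the text makes letters change between subjects, so fixed letters are the natural reading, though not an express statement.

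**Exposure.** There is one vital-sign reading before and three after the beverage per test day. Over three days that is 3 × 3 = 9 post-beverage readings per subject, three under each letter.

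**How fast could a letter be learned?** The documents state no sample size, no vital-sign effect and no SD, so there is no figure to reproduce. The calculation below is an illustration, and these inputs are assumptions:
- Each subject gives one change score per product, with normal, independent errors and SD 1 (the within-subject SD of a single product's score).
- The low-caffeine product shifts the score by 0 and both caffeinated products shift it by *d*.
- The tester averages by letter over *n* subjects and names the letter with the lowest mean.

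With φ and Φ the standard normal density and distribution function, the chance of naming the right letter is

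P = ∫ φ(z) · [Φ(d√n − z)]² dz.

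At d = 0 this is 1/3. At d = 0.5 and n = 10, d√n = 1.58 and P = 0.784. At n = 20, d√n = 2.24 and P = 0.901.

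| d | n = 1 | n = 10 | n = 20 | n = 40 | n for 90% |
|---|---|---|---|---|---|
| 0.2 | 0.39 | 0.52 | 0.60 | 0.71 | 125 |
| 0.3 | 0.42 | 0.62 | 0.73 | 0.85 | 56 |
| 0.5 | 0.48 | 0.78 | 0.90 | 0.98 | 20 |

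A simulation of the same model with 200,000 runs agrees to within 0.003; the largest gap is 0.787 against 0.784 at d = 0.5, n = 10.

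**Sensitivity to the e+shot.** Its caffeine content is not given, because the extract amounts in Table 1 are proprietary. If it shifts the score by only d/2, one factor in the integrand becomes Φ(d√n/2 − z). After 10 and 20 subjects P is then 0.54 and 0.62 at d = 0.3, and 0.66 and 0.76 at d = 0.5.

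**Sensitivity to the SD definition.** If *d* is counted in SDs of the difference between two products, *d* is replaced by d√2. P after 10 and 20 subjects is then 0.73 and 0.85 at d = 0.3, and 0.90 and 0.98 at d = 0.5. The scale must be stated whenever such figures are quoted.

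**With subject-specific codes.** Nothing can be pooled across subjects, so n stays at 1 and P is 0.39 to 0.48 over the same range of *d*. Vital-sign cues are reduced but not removed.

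**The case against.** The strongest reply is that the plan does not describe the chain of events the concern needs. A reader might infer that one researcher hands out the lettered drink, takes the readings and runs the other tests, and so will learn the letter and be unblinded for all later subjects. The documents do not support that. They mention a researcher in charge of collecting data and a research assistant, but not who dispenses, who sees the letter, who measures vital signs, or whether one tester sees many subjects. The model also assumes that someone tracks readings by letter, which nothing in the plan suggests. This objection stands, and it is why the point is conditional.

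Three further points also stand:
- Vital signs could at most single out the low-caffeine letter. In the model the e+shot and the 100 mg product stay masked from each other.
- With a small effect the guess remains unreliable for dozens of subjects. The contrast is itself unclear, because the Design statement gives the low product 25 mg of caffeine while Table 1 heads a column as placebo without caffeine. Those passages must be reconciled.
- The route from a tester's hunch to the data is narrow for much of the battery. The four cognitive tasks are computerised and take 2 + 2 + 5 + 16 = 25 of the 36 minutes, mood and energy are self-reported, and cortisol comes from saliva.

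The objection does not remove the weakness in the labelling itself. If the letters are fixed, one inference or one disclosure reaches every subject, and the plan states no safeguard against that.

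**Conclusion.** The point holds as a minor design weakness and a gap in the description. The plan appears to use one fixed letter per product and leaves open who sees it and who holds the key. If a tester sees letters and readings together, partial unblinding can build up. Over the assumed range of 0.2 to 0.5 SD, the low-caffeine letter is identified with probability 52% to 78% after 10 subjects and 60% to 90% after 20, and less if the e+shot effect is smaller. Codes unique to each subject hold this at 39% to 48%. All of these figures rest on assumed effects and on subject numbers that the documents do not give.

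The documents do not show that the blind will fail, that testers will know the allocation, or that the comparison of the e+shot with 100 mg caffeine would be exposed by vital signs. Only disclosure of the key would expose all three products.

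**What to change.** Replace the A, B and C labels with a code unique to each subject and test day. The codes should be prepared from the randomisation list by the supplier or by someone already outside the testing team, with the key withheld from testers until database lock. State in Days 2-4 who holds the key and who sees the label. If subject-specific codes or a separate assessor are already in use, a sentence saying so, and naming the role that holds the key, settles the point.

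The cost is relabelling and a code list; sample size, visits and analysis do not change. The downside is a small added risk of dispensing error, controlled by a check at hand-out. This is a cheap improvement, not a condition for the trial to be interpretable.
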